8.10.2 Assessments during Treatment

Under no circumstances will participants who enroll in this study and have completed treatment as specified, be permitted to be allocated a new Subject Number and re-enroll in the study.

All assessments must be performed as per SoA (see Section 1.3). Assessments scheduled on the day of study treatment administration should be performed prior to administration of study treatment, unless otherwise noted in the schedule of assessments.

8.10.3 Assessments at Study Completion/Early Termination Visit

Participants who complete the study or discontinue from the study early will be asked to return to the clinic 15 to 20 days after the last dose of study treatment for a follow-up visit.

8.10.4 Follow-Up Assessments

After the study completion/early termination visit, adverse events should be followed as outlined in Sections 8.3.1 and 8.3.3.

[figure not shown]
9. STATISTICAL CONSIDERATIONS

9.1 STATISTICAL HYPOTHESES

The study is an exploratory one, and there are no formal null hypotheses to be tested.

9.2 SAMPLE SIZE DETERMINATION

Fourteen *to eighteen* participants will be enrolled in order to obtain at least 12 evaluable participants. This sample size has been chosen to ensure that the ratios of the treatment geometric means can be estimated with sufficient precision.

9.3 POPULATIONS FOR ANALYSES

For purposes of analysis, the following populations are defined in [Table 6](#).

Table 6 Analysis Populations

Population	Description
Safety	All participants who have been administered study treatment and who received at least one dose of the study treatment, whether prematurely withdrawn from the study or not, will be included in the safety analysis.
Pharmacokinetic	All participants who have received at least one dose of study treatment and who have data from at least one post-dose sample will be included in the PK analysis population. Participants will be excluded from the PK analysis population if they significantly violate the inclusion or exclusion criteria, deviate significantly from the protocol, or if data are unavailable or incomplete which may influence the PK analysis. Excluded cases will be documented together with the reason for exclusion. All decisions on exclusions from the analysis will be made prior to database closure.

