6.3 MEASURES TO MINIMIZE BIAS: RANDOMIZATION AND BLINDING

6.3.1 Method of Treatment Assignment

The study is open-label. Up to 18 healthy participants will be enrolled in this study. The participant numbers will be allocated sequentially in the order in which the participants are included. The subject numbers will be generated by the Sponsor or its designee and it will be sent to the Investigator.

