9.6 SUMMARIES OF CONDUCT OF STUDY

All protocol deviations will be listed. Data for study drug administration and concomitant medications will be listed. The number of participants who were enrolled, discontinued, and completed the study will be summarized and listed.

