2.3. Exploratory objectives

The exploratory objectives are:

- To screen for the presence of RO7017773-derived metabolites.
- To assess the relative abundance and PK parameters of any metabolite as appropriate.
- To investigate whether genetic variants of drug-metabolizing enzymes (e.g. CYP3A4) can be related to the pharmacokinetic behavior or observations on the safety of RO7017773 in combination with itraconazole.

3. Study methodology

This is a single-center, non-randomized, open-label, one-sequence, two-period crossover study in healthy male and female participants:

- In Period 1, participants will be administered a single oral dose of RO7017773 alone in fed state.
- In Period 2, after a wash-out period of 10 days, participants will receive multiple doses of itraconazole in fed state for 9 days and be administered RO7017773 in combination with itraconazole. The

dose for Itraconazole will be 200 mg BID (12 hours apart) on Day 1 and 200 mg QD from Day 2 to Day 9.

[figure not shown]

As individual discontinuation criteria were not met, and the safety and tolerability profile was considered acceptable during the review of safety, tolerability and PK data of Cohort A, the subjects of Cohort B will be dosed with the same dose like Cohort A (RO7017773 [REDACTED]).

The flow chart and the schedule of assessments are available in section 14.1.

4. Sample Size

Fourteen to eighteen participants will be enrolled in order to obtain at least 12 evaluable participants. This sample size has been chosen to ensure that the ratios of the treatment geometric means can be estimated with sufficient precision.

5. Changes to the planned analysis from protocol

Not Applicable

6. Statistical considerations

Demography and safety data will be analysed using SAS® software version 9.4 or higher (SAS institute Inc. Cary NC USA).

Pharmacokinetic data will be analysed using Phoenix® WinNonlin® version 8.1 or higher (Certara USA, Inc., Princeton, NJ) and SAS® software version 9.4 or higher (SAS Institute Inc. Cary NC USA).

Descriptive statistics will be supplied according to the nature of the criteria:

- Quantitative variable: sample size, arithmetic mean, standard deviation (SD), standard error of the mean (SEM), minimum, median and maximum, and quartiles if necessary [with geometric mean, arithmetic and geometric coefficients of variation (CV), and quartiles for PK parameters].

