7.1. Definition of analysis sets

The following analysis sets will be defined:

Included set (IS): all of the subjects included in the study.

Safety set (SS): all participants who have been administered study treatment and who received at least one dose of the study treatment, whether prematurely withdrawn from the study or not, will be included in the safety analysis.

Pharmacokinetic set (PKS): all participants who have received at least one dose of study treatment and who have data from at least one post-dose sample will be included in the PK analysis population. Participants will be excluded from the PK analysis population if they significantly violate the inclusion or exclusion criteria, deviate significantly from the protocol, or if data are unavailable or incomplete which may influence the PK analysis. Excluded cases will be documented together with the reason for exclusion. All decisions on exclusions from the analysis will be made prior to database closure.

The analysis sets will be precisely defined and validated during the data review meeting.

The safety and pharmacokinetic sets will be analysed using subjects as treated.

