7.3. Protocol deviations

A summary table with the number and percentage of subjects presenting deviations relating to inclusion/exclusion criteria will be prepared overall for the subjects in the included set. A summary table with the number and percentage of subjects presenting other protocol deviations (all deviations judged relevant during the data review meeting) will also be

prepared overall by status of the deviations (minor/major). The corresponding listings will be provided with the status of the deviations.

8. Demographic data and baseline characteristics

The analyses of the demographic and baseline characteristics will be performed on the safety set.

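### Judgement-based PK-set exclusions in this open-label study need only precede database closure, and no GMR with the exclusions restored is planned

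*Protocol*

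**What the plan says.** Protocol 9.3 (Table 6), repeated in SAP 7.1, admits to the PK population anyone with one dose and one post-dose sample, then takes people out: "Participants will be excluded from the PK analysis population if they significantly violate the inclusion or exclusion criteria, deviate significantly from the protocol". A further ground is missing or partial data thought able to affect the PK results. Neither document defines a significant violation or deviation. On timing, the protocol says "All decisions on exclusions from the analysis will be made prior to database closure". The SAP adds "The analysis sets will be precisely defined and validated during the data review meeting", and SAP 1 requires SAP sign-off only before the database is locked.

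Protocol 6.3.1 states "The study is open-label", and everyone follows the same sequence. SAP 3 reports that "the safety and tolerability profile was considered acceptable during the review of safety, tolerability and PK data of Cohort A".

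SAP 9 runs the PK analysis on the PK set. The SAP's list of outputs (Appendix 2) has one drug-interaction analysis, on that set.

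The plan has some transparency measures. SAP 7.2 lists excluded participants with reasons. SAP 9.2.2 lists concentrations and PK parameters for excluded participants too. The output list carries both (16.2.3 and 16.2.5.2.1.4) on the Included set.

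On deviations, protocol 9.6 says "All protocol deviations will be listed". SAP 7.3 describes its summary of deviations other than eligibility as covering "all deviations judged relevant during the data review meeting" and promises corresponding listings. SAP 5 declares no changes from the protocol.

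**The concern.** Fixing analysis sets before lock is a strong safeguard when the deciders do not know treatment. Here Period 1 is always RO7017773 alone and Period 2 is always the combination, so anyone holding concentrations can form each participant's ratio. The criteria leave room for judgement, and one of them turns on whether incomplete data may influence the PK analysis, which invites a look at the profiles.

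The GMRs for Cmax and AUC with their 90% CIs are the planned inferential result for the primary objective, and they rest on 12 to 18 pairs. If exclusions depend on the ratios, the GMR can move and the interval becomes too narrow. The plan contains no analysis that would put such an effect in front of the reader.

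**Working it through.** **What can be reproduced.** The plan gives 14 to 18 enrolled for at least 12 evaluable. No within-subject CV or precision target is visible, so that number cannot be re-derived. The gap is 14 − 12 = 2 to 18 − 12 = 6 participants (2/14 = 14.3% to 6/18 = 33.3%). It has to absorb withdrawals as well as exclusions.

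**Model.** With both periods observed, the model in SAP 9.2.2 reduces to a paired analysis of the log ratios d:
- GMR = exp(mean of d)
- 90% CI = exp(mean of d ± t(0.95, n−1) × SD/√n)

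**Assumption.** SD of d = 0.2 to 0.4. Coverage does not depend on this value. The GMR factor does: factor = exp(shift × SD), with the shift in SD units.

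**Simulation.** At least 100,000 draws of 14 normal log ratios per case. The interval is recomputed after the exclusions, and coverage of the true mean is recorded.

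*Realistic selection.* Two or three participants have a borderline deviation unrelated to their ratio. Each is dropped only if the ratio looks unwelcome.

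| Rule | Coverage | Shift (SD units) | GMR factor, SD 0.2 to 0.4 |
|---|---|---|---|
| 2 borderline, dropped if above the mean | 89.6% | −0.062 | 0.988 to 0.976 |
| 3 borderline, dropped if above the mean | 88.7% | −0.096 | 0.981 to 0.962 |
| 2 borderline, dropped if more than 1 SD away | 87.7% | 0 | 1.00 |
| 3 borderline, dropped if more than 1 SD away | 86.4% | 0 | 1.00 |

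Example: exp(−0.096 × 0.4) = 0.962.

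*Outer bound.* Any participant may be deleted at will.

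| Rule | Coverage | Shift (SD units) | GMR factor, SD 0.2 / 0.3 / 0.4 |
|---|---|---|---|
| 1 most discordant deleted | 80% | 0 | 1.00 |
| 2 most discordant deleted | 76% | 0 | 1.00 |
| 2 highest ratios deleted | 72% | −0.243 | 0.95 / 0.93 / 0.91 |

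Deleting the most discordant participants narrows the interval (by 11% for one and 18% for two, on average) without shifting the GMR. With 18 pairs the three coverages are 82%, 77% and 74%.

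*Control.* Dropping one or two participants at random keeps coverage at 90%. The loss comes from selection, not from the smaller n.

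**Scale.** With SD 0.3 and 14 pairs, the CI limits lie at the GMR times or divided by exp(1.771 × 0.3/√14) = exp(0.142) = 1.15. The realistic shift at that SD, at most exp(−0.096 × 0.3) = 0.972, is small against this.

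**The case against.** **A reader might infer that exclusions will be made with every ratio in view.** The documents do not show this. The Cohort A review is recorded, but the visible text does not give the cohort size, the periods covered or the reviewers. It does not show that Period 2 to Period 1 ratios were formed, or that the reviewers also settle the PK set. The nearby text is redacted in places, so one can say only that no visible passage withholds concentrations.

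**A reader might infer that selective exclusion could not be detected.** That is too strong. Excluded participants, their reasons and their PK parameters are all listed, and with at most 18 participants the ratio can be recomputed by hand. What is missing is a planned, printed result.

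**A reader might take 72% to 80% coverage as the expected damage.** Table 6 has no outlier rule. An extreme participant must also have a qualifying violation, deviation or data gap, and dosing is supervised on site (protocol 6). The first table above is the fairer guide.

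**A reader might see a flat contradiction between SAP 7.3 and protocol 9.6.** The relevance filter is attached to the summary table, and SAP 5 claims no change from the protocol, so the full listing may still be intended. The listing that corresponds to a filtered table is ambiguous, however. It matters because a full list is what shows whether a similar deviation was tolerated in a retained participant.

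The study is also exploratory with no hypothesis to test (protocol 9.1), and the outcome is an assayed concentration. That lowers the severity. It does not remove the case for protecting the interval that will be reported.

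**Conclusion.** The gap is real but limited. The exclusion criteria are judgement-based, the only deadline does not separate the decision from the results in an open-label study, and the GMR is planned on the PK set alone. Outcome-informed exclusion is possible, not documented.

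With 14 pairs, a realistic degree of selectivity costs up to about four percentage points of coverage (86% to 90%) and multiplies the GMR by about 0.96 to 1.00. Free deletion of extreme ratios (72% to 80%, factor down to 0.91) is a bound that the written criteria do not themselves permit. These sizes rest on normal log ratios, the assumed SD of 0.2 to 0.4, and deviations unrelated to the ratio in the realistic case. Severity is moderate to low; this is a cheap improvement.

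**What to change.** 1. **Protocol Table 6 and SAP 7.1.** Decide PK-set exclusions from records of dosing, vomiting, sampling completeness and deviations, and freeze the list before RO7017773 concentrations are released to those who decide. Completeness can be judged from which samples were taken and when, without the values. A freeze cannot be fully applied to Cohort A, so record who had already seen its PK data. Leave parameter-level exclusions to the numeric rules in SAP 9.1.
2. **SAP 9.2.2.** Repeat the same PROC MIXED model with all PK-set exclusions restored, and print its GMR and 90% CI beside the primary result. Use every participant with a determinable parameter in either period, as the primary model does. Requiring both periods would mix the effect of restored exclusions with the loss of single-period data that the REML model keeps.
3. **SAP 7.3.** State that all protocol deviations are listed, as protocol 9.6 requires, with relevance shown as a flag.

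Cost: wording changes, one repeated model run and one table. The primary analysis is unchanged. The sensitivity estimate will include any genuinely disturbed profile, which is why it should not replace the primary.

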9.4 STATISTICAL ANALYSES

9.4.1 Demographics and Baseline Characteristics

Demographic and other baseline characteristics of the safety analysis population will be listed and summarized using descriptive statistics.

9.4.2 Safety Analyses

All safety analyses will be based on the safety analysis population.

Table 7 Safety Statistical Analysis Methods

Endpoint	Statistical Analysis Methods
Adverse events	The original terms recorded on the eCRF by the Investigator for adverse events will be coded by the Sponsor. Adverse events will be summarized by mapped term and appropriate thesaurus level.
Clinical laboratory tests	All clinical laboratory data will be stored on the database in the units in which they were reported. Laboratory test values will be presented in International System of Units (SI units; Système International d'Unités) by individual listings with flagging of abnormal results.
Vital signs	Vital signs data will be presented by individual listings with flagging of values outside the normal ranges and flagging of abnormalities. In addition, tabular summaries will be used, as appropriate.
ECG data analysis	ECG data will be presented by individual listings. In addition, tabular summaries will be used, as appropriate.
Concomitant medications	The original terms recorded on the participants' eCRF by the Investigator for concomitant medications will be standardized by the Sponsor by assigning preferred terms. Concomitant medications will be presented in summary tables and listings.
Columbia Suicide-Severity Rating Scale (C-SSRS)	Individual data at will be presented in listings.

9.4.3 Pharmacokinetic Analyses

Analyses will be carried out on the PK analysis population.

9.4.3.1 Pharmacokinetic Parameters

The primary RO7017773 PK study variable will be the AUC (AUC_{0-inf} if it can be derived, otherwise truncated as appropriate) and C_{max}. All other PK parameters will be regarded as secondary.

The following PK parameters of RO7017773 and of itraconazole and its metabolites (e.g., hydroxy-itraconazole) will be read from the concentration versus time profiles or estimated using non-compartmental methods where appropriate:

- T_{max} : Time to maximum plasma concentration
- C_{max} : maximum observed plasma concentration
- AUC_{0-t} : area under the plasma concentration-time curve up to time t
- AUC_{0-last} : area under the plasma concentration-time curve up to the last measurable concentration
- AUC_{0-inf} : area under the plasma concentration-time curve extrapolated to infinity

- $T_{1/2}$: apparent terminal half-life, computed as $\ln(2)/\lambda_z$
- CL/F: apparent oral clearance, calculated as Dose/AUC_{0-inf}
- $R_{AUC_{0-inf}}$: AUC ratios calculated as RO7017773 AUC_{0-inf} Period 2 over RO7017773 AUC_{0-inf} Period 1
- $R_{C_{max}}$: C_{max} ratio calculated as RO7017773 C_{max} Period 2 over RO7017773 C_{max} Period 1
- C_{trough} : trough (pre-dose) plasma concentration for itraconazole and its metabolites hydroxy-itraconazole.

Additional PK parameters may be reported as appropriate.

All pharmacokinetic concentration and calculated PK parameters for RO7017773, itraconazole and its metabolite will be presented in individual listings and summary tables (including descriptive summary statistics: mean, standard deviation, coefficient of variation, median, minimum, and maximum), and graphs (including concentration vs. time plots on linear and semi-logarithmic scales) as appropriate.

9.4.3.2 Statistical Analysis

The following linear statistical model will be applied to the log-transformed, dose-normalized PK variables AUC (AUC_{0-∞} if it can be derived, otherwise truncated as appropriate) and C_{max} :

$$y_{ij} = \mu + \tau_j + s_i + \varepsilon_{ij} \quad (i = 1, 2, \dots, 12; j = 1, 2)$$

where μ denotes the general mean of the transformed variables, τ_j is the effect of the treatment (RO7017773 alone vs. RO7017773 together with Itraconazole), s_i is the random subject effect and ε_{ij} is the random error (within subject variability). The random subject effect and the random error are assumed to be independent and normally distributed with zero means and variances σ_s^2 and σ_ε^2 respectively.

Least square means with corresponding 90% confidence intervals (CI) will be derived to compare the relative bioavailability of the different treatments.

Under this model the (geometric means) ratios $\frac{AUC(\text{RO7017773+IT})}{AUC(\text{RO7017773})}$ and $\frac{C_{max}(\text{RO7017773+IT})}{C_{max}(\text{RO7017773})}$

are obtained as $\frac{\mu_{\lambda_1}}{\mu_{\lambda_2}} = e^{\lambda_1 - \lambda_2}$, i.e. by exponentiation of the corresponding estimated

differences in the analysis of variance (ANOVA) model.

9.5 INTERIM ANALYSES

No interim analyses are planned for this study.

9.6 SUMMARIES OF CONDUCT OF STUDY

All protocol deviations will be listed. Data for study drug administration and concomitant medications will be listed. The number of participants who were enrolled, discontinued, and completed the study will be summarized and listed.

11. SUPPORTING DOCUMENTATION AND OPERATIONAL CONSIDERATIONS

The following section includes standard appendices such as [Appendix 1](#) (for regulatory, ethical and study oversight considerations), [Appendix 2](#) (for AE definitions, reporting) and [Appendix 3](#) (procedures of recording), [Appendix 5](#) (contraceptive guidance and collection of pregnancy information). Additional study-related appendices are in order of appearance in the protocol.

Appendix 1 **Regulatory, Ethical, and Study Oversight Considerations**

1. REGULATORY AND ETHICAL CONSIDERATIONS

1.1. COMPLIANCE WITH LAWS AND REGULATIONS

This study will be conducted in full conformance with the ICH E6 guideline for Good Clinical Practice and the principles of the Declaration of Helsinki, or the laws and regulations of the country in which the research is conducted, whichever affords the greater protection to the individual. The study will comply with the requirements of the ICH E2A guideline (Clinical Safety Data Management: Definitions and Standards for Expedited Reporting). Studies conducted in the United States or under a U.S. Investigational New Drug (IND) application will comply with U.S. FDA regulations and applicable local, state, and federal laws. Studies conducted in the EU/EEA will comply with the EU Clinical Trial Directive (2001/20/EC).

1.2. INSTITUTIONAL REVIEW BOARD OR ETHICS COMMITTEE

This protocol, the ICFs, any information to be given to the participant (e.g. advertisements, diaries etc.), and relevant supporting information must be submitted to the IRB/EC by the Principal Investigator and reviewed and approved by the IRB/EC before the study is initiated.

The Principal Investigator is responsible for providing written summaries of the status of the study to the IRB/EC annually or more frequently in accordance with the requirements, policies, and procedures established by the IRB/EC. Investigators are also responsible for promptly informing the IRB/EC of any protocol amendments (Section [2.3.1](#) of this Appendix).

The Investigator should follow the requirements for reporting all adverse events to the Sponsor. Investigators may receive written IND safety reports or other safety-related communications from the Sponsor. Investigators are responsible for ensuring that such reports are reviewed and processed in accordance with Health Authority requirements and the policies and procedures established by their IRB/EC, and archived in the site's study file.

1.3. INFORMED CONSENT

The Sponsor's Master Informed Consent Form (and ancillary sample ICFs such as a Child's Assent or Caregiver's Informed Consent Form, if applicable) will be provided to each site. If applicable, it will be provided in a certified translation of the local language. Participants must be informed that their participation is voluntary. Participants will be required to sign a statement of informed consent that meets the requirements of 21 CFR 50, local regulations, ICH guidelines, Health Insurance Portability and Accountability Act (HIPAA) requirements, where applicable, and the IRB/IEC or study center. The Sponsor or its designee must review and approve any proposed deviations from the Sponsor's sample ICFs or any alternate consent forms proposed by the site (collectively, the "Consent Forms") before IRB/EC submission. The final IRB/EC-approved Consent Forms must be provided to the Sponsor for Health Authority submission purposes according to local requirements. Participants must be re-consented to the most current version of the ICF(s) during their participation in the study. A copy of the ICF(s) signed by all parties must be provided to the participant.

The Consent Forms must be signed and dated by the participant or the participant's legally authorized representative before his or her participation in the study. The case history or clinical records for each participant shall document the informed consent process and that written informed consent was obtained prior to participation in the study.

The Consent Forms should be revised whenever there are changes to study procedures or when new information becomes available that may affect the willingness of the participant to take part. The final revised IRB/EC-approved Consent Forms must be provided to the Sponsor for Health Authority submission purposes if required as per local regulations.

Participants must be re-consented to the most current version of the Consent Forms (or to a significant new information/findings addendum in accordance with applicable laws and IRB/EC policy) during their participation in the study. For any updated or revised Consent Forms, the case history or clinical records for each participant shall document the informed consent process and that written informed consent was obtained using the updated/revised Consent Forms for continued participation in the study.

A copy of each signed Consent Form must be provided to the participant or the participant's legally authorized representative. All signed and dated Consent Forms must remain in each participant's study file or in the site file and must be available for verification by study monitors at any time.

